³ The mean and SD of the per patient difference in infection-related AEs that occurred during the specified onset periods is presented.

⁴ The median of the per patient difference in infection-related AEs that occurred during the specified onset periods is presented.

⁵ 2-sided p-value based on a Wilcoxon Signed-Rank test of the difference in the number of infection-related AEs per subject between the first and second periods (null hypothesis defined as zero for difference).

2.2.6. The effect of dose on outcomes has been studied (see Figure 3). The outcomes evaluated have included CD4 count, naïve CD4 T cell number, the T cell proliferation response to the mitogen phytohemagglutinin (PHA), and the T cell receptor beta variable (TCRBV) diversity at one year. [Note: TCRBV variability is measured using spectratyping and is reported as the Kullback-Leibler divergence (D_{KL}) score. The lower the D_{KL} , the more normal the diversity. High D_{KL} reflect limited diversity. Normal adults have D_{KL} s around 0.1. Abnormal D_{KL} values can be >1.0.] The graphs below show the one-year results from previous subjects for whom we have measured dose data who are beyond 1 year after thymus transplantation. The T cell number and PHA data reflect the mean of the first two values beyond year one. The D_{KL} data are a single time point at approximately year one. The correlation coefficients are poor and none approach significance. The lack of significance holds if the data are analyzed separately for the groups with suppression and without suppression.

[figure not shown]

Figure 3. Lack of effect of dose on immune outcomes. A) Dose plotted versus the CD4 count at 1 year. B) The effect of dose on naive CD4 cells at one year. C) Dose plotted versus the statistical measure of TCRBV diversity, D_{KL} , at one year. D) Dose versus the PHA response at one year. Trend lines are shown. ([name] et al, 2008b Am J Transplantation)

2.2.7. The relationship between matching at HLA-DR and immune outcomes has been tested. No significance has been found. ([name] et al, 2008b Am J Transplantation)

2.2.8. Rationale for use of immunosuppression.

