This is an ongoing Phase I/II, single site, open, nonrandomized clinical protocol conducted at Duke University Medical Center. The principal investigator/sponsor is [REDACTED] Subjects will receive a postnatal cultured allogeneic thymus transplant with or without immunosuppression prior to transplantation. Subjects will be enrolled in one of four Groups. All subjects will have been diagnosed as having complete DiGeorge anomaly, characterized by very low T cell numbers (<50/mm³) or less than 50/mm³ naïve T cells (CD3+CD45RA+CD62L+) or naïve T cells being less than 5% of total T cells.

The primary efficacy endpoint for this study will be survival at one year post-transplant. Additional efficacy endpoints will include naïve CD4 T cell counts at 12 months post-transplant and the following variables assessed at 6 and 12 months post-transplant: total CD3, total CD3+CD4+, total CD3+ CD8+, total naïve CD3+ CD4+, total naïve CD3+ CD8+, total TCR $\alpha\beta$ and TCR $\gamma\delta$ T cells, total B and NK cells. Proliferative T cell responses in counts per minute (cpm) to phytohemagglutinin and tetanus toxoid (if done) and TCR repertoire variability by flow cytometry of CD3+ CD4+ cells will also be assessed at one year post-transplant. If an allograft biopsy is performed, the following will be assessed at the time of biopsy: presence of thymopoiesis, presence of Hassall bodies, and presence of graft rejection.

Studies 735, 33170, and 51692:

Non-core IND 9836 protocols for BLA were also conducted and will contribute subjects to the FAS (Table 2.1). Synoptic study reports including available demographic, survival, and safety information (adverse events and serious adverse events) will be developed. All available data will be listed.

CONFIDENTIAL

3 Objectives

The objectives of all studies was to investigate the safety and efficacy of thymus transplantation in complete DiGeorge Anomaly patients. Each study had slightly different objectives, but in general, the goal was to examine survival and immune system response at 1 year post transplantation. The studies all followed subjects through two years post-transplant, thus objectives will also be summarized at 2 years post-transplant.

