5.1 Planned Analyses

There are three analysis populations defined for these studies: the efficacy analysis set (EAS), modified efficacy analysis set (EAS-cDGA), and the full analysis set (FAS), which are defined in Section 3.5. Efficacy analyses will be carried out using the EAS and EAS-cDGA. The demographic and safety analysis will be carried out on the FAS.

Summary statistics will be presented for continuous variables, by way of n, mean, standard deviation (SD), median, quartiles, and ranges and by way of frequencies and percentages for categorical variables.

Survival will be evaluated one year and two years post-transplant.

All statistical analyses will be performed in SAS version 9.4 or later running on a validated platform.

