5.7.2 Methods of analysis for secondary outcomes

Immune outcomes and dose effect are assessed after thymus transplantation by examining biopsies of the allografts by immunohistochemistry; flow cytometry; assessing variability of the T cell receptor beta gene variable (TCR β V) region; assessing T cell proliferative responses and measuring B cell antibody responses to antigens. Descriptive summaries will be provided at Year 1, and if available at Year 2.

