5.8.2 Safety and Efficacy Laboratory findings

Results from the following laboratory parameters (5.8.2.1 and 5.8.2.2) will be summarised using the value at each visit and change from baseline at each visit.

Categorical and numeric variables will be presented separately.

Clinically significant treatment-emergent laboratory findings will be summarised as adverse events.

Notes:

- All results outside predefined normal ranges will be flagged in the data listings.

CONFIDENTIAL

Sponsor:	Enzyvant Therapeutics GmbH	Program:	RVT-802
----------	----------------------------	----------	---------

- Repeat laboratory results within a visit will not be used in any summary calculations. Unscheduled (those obtained outside of the safety analysis windows defined in Section 4.3.2) and repeat results will be listed only.
- Any other laboratory results will be listed only.

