5.8.2.2 Clinical Efficacy Laboratories

Serum Immunoglobulins and Isohemagglutinins:

IgG, IgA, IgM, IgG, Anti-A, and Anti-B.

Flow Cytometry:

Percentage of ALC, CD3, CD4, CD8, DB Neg, TCR $\alpha\beta$, TCR $\gamma\delta$, B, NK, Naïve CD3, Naïve CD4, and Naïve CD8 cells.

Number of ALC, CD3, CD4, CD8, DB Neg, TCR $\alpha\beta$, TCR $\gamma\delta$, B, NK, Naïve CD3, Naïve CD4, and Naïve CD8 cells.

TCR Flow:

VB1, VB2, VB3, VB4, VB5.1, VB5.2, VB5.3, VB7.1, VB7.2, VB7, VB8, Vb8.1/8.2, Vb9, VB11, VB12, VB13.1, VB13.2, VB13.6, VB14, VB16, VB17, VB18, Vb20, VB21.3, VB22, and VB23.

Proliferation Assay:

PT CONA, PT CONA BKG, CONTROL CONA, CONTROL CONA BKG, PT SOL CD3, PT SOL CD3 BKG, PT INSOL CD3 PT INSOL BKG, PT IMMOB CD3, PT IMMOB CD3 BKG, CONTROL SOL CD3, CONTROL SOL CD3 BKG CONTROL IMMOB CD3, CONTROL

CONFIDENTIAL

Sponsor:	Enzyvant Therapeutics GmbH	Program:	RVT-802
----------	----------------------------	----------	---------

IMMOB CD3 BKG, PT TT, PT TT BKG (PT AG BKG), CONTROL TT, CONTROL TT BKG (CTRL AG BKG), PT CANDIDA, PT CANDIDA BKG, CONTROL CANDIDA, and CONTROL CANDIDA BKG.

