6.3.2 Section 14.2: Efficacy

The tables below will be created using the EAS-cDGA, EAS, and FAS.

Table 14.2.1.1.1	Summary of Kaplan-Meier Survival
Table 14.2.1.1.14	Summary of Kaplan-Meier Survival (Day of Life)
Table 14.2.1.2.1	Kaplan-Meier Survival by Year
Table 14.2.1.2.14	Kaplan-Meier Survival by Year (Day of Life)
Table 14.2.1.3.1	Binomial Exact Test of Survival at Year 1 Post-Transplantation
Table 14.2.1.3.2	Binomial Exact Test of Calcium Use at Year 1 Post-Transplantation*
Table 14.2.1.3.14	Binomial Exact Test of Survival at Year 2 Post-Transplantation
Table 14.2.2.1.1	T Cell Count - Flow Cytometry
Table 14.2.2.2.1	Biopsy
Table 14.2.2.3.1	T Cell Proliferation
Table 14.2.2.4.1	Immunoglobulins
Table 14.2.2.5.1	B Cell Function Elevation
Table 14.2.2.6.1	TRECs
Table 14.2.2.7.1	TREGs
Table 14.2.2.8.1	T Cell Receptor Diversity (Immunoscope / Spectratyping)
Table 14.2.2.9.1	Subject Infection
Table 14.2.2.10.1	T Cell Receptor Diversity (TCR Flow)

*only applies to Study 931.

[figure not shown]

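### The Year 1 TCR repertoire endpoint for Study 25966 is planned as family-by-family summaries across children, which do not measure diversity within a child or count the children who have it

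*SAP*

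**What the plan says.** Protocol 4.1.2 lists TCR repertoire variability among the secondary endpoints at Year 1, as far as data permit. For Study 25966 the SAP (section 2) names the assay: "TCR repertoire variability by flow cytometry of CD3+ CD4+ cells will also be assessed at one year post-transplant".

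The processing is in SAP 5.8.2, where the listed laboratory parameters "will be summarised using the value at each visit and change from baseline at each visit". Under TCR Flow, SAP 5.8.2.2 lists 26 V-beta entries, beginning "VB1, VB2, VB3, VB4, VB5.1, VB5.2, VB5.3, VB7.1, VB7.2, VB7, VB8". SAP 5.1 gives the statistics for continuous variables: "by way of n, mean, standard deviation (SD), median, quartiles, and ranges". SAP 5.7.2 makes the analysis descriptive: "Descriptive summaries will be provided at Year 1, and if available at Year 2".

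The output is Table 14.2.2.10.1 (SAP 6.3.2), whose title presents it as T cell receptor diversity by flow. Child-level values go to Listing 16.2.8.11. The SAP text defines no per-child score, reference distribution or count of diverse children for the flow assay.

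Elsewhere the programme treats diversity as a per-child property. Protocol 2.2.4 reports a polyclonal repertoire in 41 of 43 survivors beyond one year. In Protocol 2.2.6, "TCRBV variability is measured using spectratyping and is reported as the Kullback-Leibler divergence", and the SAP names the same score for Study 950. Both uses are spectratyping. SAP 6.3.2 has a programme-level spectratyping table (14.2.2.8.1), but neither document schedules spectratyping for 25966.

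**The concern.** Whether a repertoire is diverse depends on how one child's T cells are spread over the V-beta families. Averaging one family over children answers a different question: how common that family is in the cohort. Expansions of different families in different children can cancel in the family means, and a set of per-family distributions does not show which values belong to the same child.

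The distinction matters in this disease. The protocol describes atypical complete DiGeorge anomaly by its oligoclonal T cells (2.2.8.1, 2.6.1.5), expects pre-transplant TCRBV flow to show oligoclonality in atypical subjects (5.1.3.1.4.4), and cites receptor diversity at one year as an indicator of successful reconstitution (section 3). A reader will want to know how many children reached a diverse repertoire and how far each moved from baseline. The planned table gives neither.

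**Working it through.** The plan states no figure for this endpoint, so there is none to reproduce. The check is by construction: can cohorts that differ in within-child diversity give the same planned statistics?

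**Inputs.** 26 V-beta entries (SAP 5.8.2.2); 24 subjects transplanted in 25966 (SAP Table 2.1); n, mean, SD, median, quartiles and range (SAP 5.1).

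**Assumptions.** Values are percentages that sum to 100 within a child. Examples 1 and 2 use 24 non-overlapping families: 26 entries, less VB7 (covered by VB7.1 and VB7.2) and less one of VB8 and Vb8.1/8.2. The cohorts are constructed, not observed.

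**1. Means alone.** 24 children, each with a different family at 60% and the other 40% spread evenly (40/23 = 1.74% each).
- Mean of every family: (60 + 23 × 1.739)/24 = 4.17%, equal to the even value 100/24.
- Divergence of each child from an even repertoire: 0.6 ln(0.6 × 24) + 0.4 ln(0.01739 × 24) = 1.600 − 0.349 = 1.25, against 0 for an even child.
- Effective number of families per child, 1/Σp²: 1/(0.36 + 23 × 0.01739²) = 2.7, against 24.
- The other planned statistics do move. Every family has median 1.74% instead of 4.17%, SD 11.9 points and maximum 60%.

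**2. A mixed cohort.** 18 assessed children: 4 as above, in four different families, and 14 even.
- Affected families: (60 + 3 × 1.739 + 14 × 4.167)/18 = 6.86%.
- Other families: (4 × 1.739 + 14 × 4.167)/18 = 3.63%.
- Every family has median and both quartiles at 4.17%. Only the mean, SD and range respond: SD 13.3 points and maximum 60% in the four affected families, SD 1.0 elsewhere.

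**3. All planned statistics identical.** 5 children, 25 families.
- Cohort A: one child has families 1 to 5 at 20% each and nothing else; four children have every family at 4%.
- Cohort B: child k has family k at 20%, four of families 6 to 25 absent (a different four for each child), and the other 20 families at 4%. Sum: 20 + 20 × 4 = 100.
- In both cohorts each of families 1 to 5 holds the values {20, 4, 4, 4, 4} and each of families 6 to 25 holds {0, 4, 4, 4, 4}. Mean, SD, median, quartiles and range therefore agree in every family. If all children start from the same baseline profile, the change summaries agree too.
- Effective number of families: A gives 1/(5 × 0.2²) = 5 for one child and 1/(25 × 0.04²) = 25 for four. B gives 1/(0.2² + 20 × 0.04²) = 1/0.072 = 13.9 for all five.
- Four fully even children in A, none in B.

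**4. Does a per-child index separate cohorts with equal means?** Using all 26 entries and 24 children, a polyclonal and an oligoclonal cohort were built with identical family means.

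| Family means | Median effective number, polyclonal | Median effective number, oligoclonal |
|---|---|---|
| Even (3.85% each) | 24.6 | 1.65 |
| Uneven (1.2% to 9.0%) | 20.2 | 1.72 |

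**The case against.** **The planned table would expose gross failure.** A reader might infer that a cohort in which every child is oligoclonal would pass unnoticed. The documents do not support that. SAP 5.1 requires more than means, and in example 1 the median falls to 1.74% with SD 11.9 and maximum 60%. This stands, and it limits the point to what the table fails to measure.

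**Exact cancellation is a best case.** Nothing in either document says that oligoclonal children tend to expand different families. If each of 24 children expanded a family at random, the chance of 24 different families is 24!/24^24, about 5 × 10⁻¹⁰. Simulated family means then typically ran from 1.7% to 9.0%. This also stands against example 1 as a prediction. It does not touch example 3, which shows that the full set of family statistics does not determine the child-level result.

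**Child values are already listed.** Listing 16.2.8.11 gives them, SAP 5.8.2 flags out-of-range results in listings, and there are at most 24 subjects. A reader could inspect each profile. That is a real mitigation, but it leaves the endpoint to be derived informally by the reader.

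**The endpoint is secondary, descriptive and sparse.** Post-transplant TCRBV flow is optional (Protocol 6.2.1.8.3.3), and the pre-transplant assay needs enough T cells (6.2.1.4.11). No hypothesis or stopping rule uses it. This limits the consequence.

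**A score could sit in the table shells.** They are not in the documents, and SAP 6.3 says the table list will be adapted by study. A derived measure cannot be excluded, but none is specified in the SAP text.

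**No control reference is available.** SAP 5.8.2.2 lists control values for proliferation assays and none for TCR flow. The argument stands against making a healthy-control divergence the default fix. The spectratyping benchmarks in Protocol 2.2.6 do not transfer to V-beta family shares.

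**Conclusion.** The concern holds in a limited form. As specified, Table 14.2.2.10.1 reports how each V-beta family is distributed over children. It cannot give diversity within a child, its change from baseline, or the number of children with a diverse repertoire. Equal means can arise from cohorts with about 2.7 and 24 effective families per child, and cohorts with four and with no fully even children can agree on every planned statistic.

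This rests on the SAP text without table shells, on flow values being shares within a child, and on constructed cohorts that show what is possible, not what is likely. It does not support saying that the table would hide a uniformly oligoclonal cohort, or that medians could not reveal one. The primary survival analysis is unaffected.

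**What to change.** In SAP 5.8.2.2 and Table 14.2.2.10.1:

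- Derive one diversity index per subject per visit from non-overlapping V-beta families plus a residual category. Do not use VB7 together with VB7.1/7.2, or VB8 together with Vb8.1/8.2.
- Use a reference-free index, such as 1/Σp² or Shannon entropy, and fix the choice before analysis.
- Summarise the index at baseline and Year 1, and its change, with the number of subjects assessed at each time and the number with both values.
- Keep the family-by-family values as supportive output.
- Add a divergence from healthy controls, and a count of subjects within the control range, only if the laboratory holds a control distribution that can be fixed before analysis.

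The cost is SAP wording and a short derivation from data already collected. The reference-free index gives a graded measure; a count of diverse children still needs a pre-set cut-off or control range. Paired values may be few because the assay is optional after transplant and baseline testing depends on sufficient T cells, so the denominators must be shown.

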5.8.3 Vital signs

A summary of vital signs for observed value and change from baseline over time will be produced using the safety analysis windows given in Table 5.3.2.1. All data will be listed.

5.9 Adjustment for Covariates

No covariates will be included in the analyses.

5.10 Missing Values – Missing Visits

No imputation of missing data will be done.

5.11 Algorithms/SAS Codes

- **Tables that need descriptive statistics – continuous variables:**

```
PROC UNIVARIATE DATA=dset NOPRINT;
  VAR var1 var2 var3 ...varn;
  BY byvar; (optional)
  OUTPUT OUT=outname
  N=n MEAN=mean MIN=min MAX=max MEDIAN=median STD=std;
RUN;
```

- **Tables that need frequency counts:**

```
PROC FREQ DATA=dset NOPRINT;
  BY byvar; (optional)
  TABLES var1*var2;
  OUTPUT OUT=outname;
RUN;
```

- **Tables that present the binomial proportion test:**

```
PROC FREQ DATA=dset NOPRINT;
  BY byvar; (optional)
  TABLES var1 / BINOMIAL (P=0.XX);
  EXACT BINOMIAL;
  OUTPUT OUT=outname;
RUN;
```

- **Tables that present Fisher's Exact or CMH:**

```
PROC FREQ DATA=dset NOPRINT;
  BY byvar; (optional)
```

CONFIDENTIAL

```
TABLES var1*var2 / CMH score=MODRIDIT EXACT;  
OUTPUT OUT=outname CMH EXACT;  
RUN;
```

- **Tables that need number of events/censored and probabilities of failure/survival at cut off times:**

```
PROC LIFETEST DATA=dset OUTSURV=LIFE METHOD=KM INTERVALS=12, 24;  
TIME duration*censor (0 or 1);  
ID subject;  
STRATA treatment;  
RUN;
```

6 Tables and Listings

6.1 Table Format

All output will be produced using SAS version 9.4 or a later version.

In the top left portion of each table/listing, a *table/listing number* followed by the *title* of the table/listing will be presented. After the title line, optional *sub-title* or *population* information can be presented. Horizontal lines will appear before and after the column heading of the table/listing. *Footnotes* will be put under the main body of text at the bottom of the page.

The *sponsor name*, *protocol number*, programmers User ID, status of the table/listing (i.e. draft or final) and *SAS program name* will appear bottom left in a string and the *page number* will appear on the bottom right corner of each table/listing. The *date and time of creation* of table/listing will appear bottom left under the sponsor name. The source listing number will appear bottom left. The *database lock date or data snapshot date* will appear bottom left.

A *landscape layout* is proposed for both table and listing presentations.

The *left and right margins* of all tables and listings will be a minimum of 2.1 cm from the left and 1.9cm from the right. The *top and bottom margins* will be a minimum 2.92cm. *Header and footer* will be both 1.27 cm.

There is no special requirement of *font type* and *size*, but an *8-point* font size for tables and listings is proposed using *Times New Roman* font. A maximum SAS line size=141 and page size=44 for *8-point* font size will be used so as to fit on both UK and US paper sizes.

In a listing, in the case that a subject's record has been continued to the next page, an appropriate identification (e.g., the subject ID number and/or visit name) must be presented at the beginning of that page.

CONFIDENTIAL

Sponsor:	Enzyvant Therapeutics GmbH	Program:	RVT-802
----------	----------------------------	----------	---------

6.2 Conventions

Unless otherwise specified, in summary tables of continuous variables, the minimum and maximum values will be displayed to the same number of decimal places as the raw data, the mean and median will be presented to one extra decimal place compared to the raw data, and the standard deviation will be displayed to two extra decimal places compared to the raw data. Wherever possible data will be decimal aligned.

Unless otherwise specified frequency tabulations will be presented by number and percentage, where the percentage is presented in brackets to 1 decimal place.

P-values, if applicable, will be presented to 3 decimal places. If a p-value is less than 0.05 but is greater than or equal to 0.01, then an asterisk (*) will be added next to this value. If a p-value is less than 0.01 but is greater than or equal to 0.001, then two asterisks (**) will be added next to this value. Finally, if the p-value is less than 0.001 then three asterisks (***) will be added next to this value and it will be presented as <0.001. If the rounded result is a value of 1.000, it will be displayed as >0.999. Any date information in the listing will use the *date9.* format, for example, 07MAY2002. In the listing, a unit associated with a variable will be presented only once within parentheses either below or next to that variable in the heading portion. If a parameter has multiple units, each unit will be displayed only once, as applicable.

All tables will have their source listing referenced in a footnote. Listings should be sorted group, subject and visit and have the source data received by data management referenced in a footnote. All tables and listings will be converted into Microsoft Word documents and collated into two complete documents.

6.3 Tables

Not all tables will be created for all studies. The list below will be adapted based on what is available and required in each study. For example, the calcium or calcitrol use at year 1 was only collected and required in study 931.

6.3.1 Section 14.1: Disposition, Exposure, and Demographics

The tables below will be created using the EAS-cDGA, EAS, and FAS.

Table 14.1.2	Subject Disposition
Table 14.1.3	Analysis Populations
Table 14.1.4.1	Demographics and Selected Baseline Characteristics
Table 14.1.4.2	Disease History
Table 14.1.5	Thymus Transplant and Dose Information
Table 14.1.6.1	Medical History
Table 14.1.6.2	Pre-Transplant Infection History
Table 14.1.7.1	Immunosuppressive Medications

CONFIDENTIAL

6.3.2 Section 14.2: Efficacy

The tables below will be created using the EAS-cDGA, EAS, and FAS.

Table 14.2.1.1.1	Summary of Kaplan-Meier Survival
Table 14.2.1.1.14	Summary of Kaplan-Meier Survival (Day of Life)
Table 14.2.1.2.1	Kaplan-Meier Survival by Year
Table 14.2.1.2.14	Kaplan-Meier Survival by Year (Day of Life)
Table 14.2.1.3.1	Binomial Exact Test of Survival at Year 1 Post-Transplantation
Table 14.2.1.3.2	Binomial Exact Test of Calcium Use at Year 1 Post-Transplantation*
Table 14.2.1.3.14	Binomial Exact Test of Survival at Year 2 Post-Transplantation
Table 14.2.2.1.1	T Cell Count - Flow Cytometry
Table 14.2.2.2.1	Biopsy
Table 14.2.2.3.1	T Cell Proliferation
Table 14.2.2.4.1	Immunoglobulins
Table 14.2.2.5.1	B Cell Function Elevation
Table 14.2.2.6.1	TRECs
Table 14.2.2.7.1	TREGs
Table 14.2.2.8.1	T Cell Receptor Diversity (Immunoscope / Spectratyping)
Table 14.2.2.9.1	Subject Infection
Table 14.2.2.10.1	T Cell Receptor Diversity (TCR Flow)

*only applies to Study 931.

[figure not shown]
